# 10.7.2. Definition of SAE, SADE, and USADE

If an event is not an AE per the definition above, then it cannot be an SAE even if serious conditions are met (eg, hospitalization for signs/symptoms of the disease under study, death due to progression of disease).

An SAE is an AE that:			
a.	Led to death		
b.	Led to serious deterioration in the health of the participant, that either resulted in:		
	1. A life-threatening illness or injury. The term "life-threatening" in the definition of		
	"serious" refers to an event in which the participant was at risk of death at the time of		
	the event. It does not refer to an event that hypothetically might have caused death if it		
	were more severe.		
	2. A permanent impairment of a body structure or a body function		
	3. Inpatient or prolonged hospitalization. Planned hospitalization for a pre-existing		
	condition, or a procedure required by the protocol, without serious deterioration in		
	health, is not considered an SAE.		
	4. Medical or surgical intervention to prevent life-threatening illness or injury or		
	permanent impairment to a body structure or a body function		
c.	Led to fetal distress, fetal death, or a congenital abnormality or birth defect		
SADE Definition			
•	A SADE is defined as an adverse device effect that has resulted in any of the consequences		
	characteristic of a serious adverse event.		
•	Any device deficiency that might have led to a serious adverse event if appropriate action		
	had not been taken, intervention had not occurred, or circumstances had been less		
	fortunate.		

#### **USADE Definition**

• A USADE is defined as a SADE which by its nature, incidence, severity or outcome has not been identified in the current version of the risk analysis report (see Section 2.3).

## CONFIDENTIAL

JUVÉDERM® VOLUMA® with Lidocaine injectable gel

#### 10.7.3. Definition of Device Deficiency

#### **Device Deficiency Definition**

• A device deficiency is an inadequacy of a medical device with respect to its identity, quality, durability, reliability, safety, or performance. Device deficiencies include malfunctions, use errors, and inadequate labeling.

#### 10.7.4. Recording and Follow-up of AE and/or SAE and Device Deficiencies

#### AE, SAE, and Device Deficiency Recording

- When an AE/SAE/device deficiency occurs, it is the responsibility of the PI to review all documentation (eg, hospital progress notes, laboratory reports, and diagnostics reports) related to the event.
- The PI will then record all relevant AE/SAE/device deficiency information in the participant's medical records, in accordance with the investigator's normal clinical practice and on the appropriate form of the eCRF.
- It is **not** acceptable for the PI to send photocopies of the participant's medical records to the sponsor or designee in lieu of completion of the sponsor or designee AE/SAE/device deficiency eCRF page.
- There may be instances when copies of medical records for certain cases are requested by the sponsor or designee. In this case, all participant identifiers, with the exception of the participant number, will be redacted on the copies of the medical records before submission to the sponsor or designee.
- The PI will attempt to establish a diagnosis of the event based on signs, symptoms, and/or other clinical information. Whenever possible, the diagnosis (not the individual signs/symptoms) will be documented as the AE/SAE.
- For device deficiencies, it is very important that the PI describes any corrective or remedial actions taken to prevent recurrence of the incident.
  - A remedial action is any action other than routine maintenance or servicing of a medical device where such action is necessary to prevent recurrence of a device deficiency. This includes any amendment to the device design to prevent recurrence.

### CONFIDENTIAL

### JUVÉDERM® VOLUMA® with Lidocaine injectable gel

#### Assessment of Intensity

The PI will make an assessment of intensity for each AE/SAE/device deficiency reported during the study and assign it to one of the following categories:

- Mild: A type of AE that is usually transient and may require only minimal treatment or • therapeutic intervention. The event does not generally interfere with usual activities or daily living.
- Moderate: A type of AE that is usually alleviated with additional specific therapeutic • intervention. The event interferes with usual activities of daily living, causing discomfort but poses no significant or permanent risk of harm to the research participant.
- Severe: A type of AE that interrupts usual activities of daily living, or significantly • affects clinical status, or may require intensive therapeutic intervention.
- An event is defined as 'serious' when it meets at least one of the predefined outcomes as described in the definition of an SAE, NOT when it is rated as severe.

#### Assessment of Causality

- The PI is obligated to assess the relationship between study intervention and each occurrence of each AE/SAE/device deficiency.
- A "reasonable possibility" of a relationship conveys that there are facts, evidence, and/or arguments to suggest a causal relationship, rather than a relationship cannot be ruled out.
- The PI will use clinical judgment to determine the relationship. •
- Alternative causes, such as underlying disease(s), concomitant therapy, and other risk factors, as well as the temporal relationship of the event to study intervention administration will be considered and investigated.
- The investigator will also consult the IDFU and IB in his/her assessment.
- For each AE/SAE/device deficiency, the PI must document in the medical notes that he/she has reviewed the AE/SAE/device deficiency and has provided an assessment of causality.
- There may be situations in which an SAE has occurred, and the PI has minimal information to include in the initial report to sponsor or designee. However, it is very important that the PI always make an assessment of causality for every event before the initial transmission of the SAE data to sponsor or designee.

#### CONFIDENTIAL JUVÉDERM® VOLUMA® with Lidocaine injectable gel

- The PI may change his/her opinion of causality in light of follow-up information and send an SAE follow-up report with the updated causality assessment.
- The causality assessment is one of the criteria used when determining regulatory reporting requirements.

#### Follow-up of AE/SAE/Device Deficiency

- The PI is obligated to perform or arrange for the conduct of supplemental measurements and/or evaluations as medically indicated or as requested by the sponsor or designee to elucidate the nature and/or causality of the AE/SAE/device deficiency as fully as possible. This may include additional laboratory tests or investigations, histopathological examinations, or consultation with other health care professionals.
- If a participant dies during participation in the study or during a recognized follow-up period, the PI will provide the sponsor or designee with a copy of any post-mortem findings including histopathology.
- New or updated information will be recorded in the originally completed eCRF.
- The PI will submit any updated SAE data to the sponsor or designee within 24 hours of receipt of the information.

#### 10.7.5. Reporting of SAEs

#### SAE Reporting to Sponsor or Designee Within 24 Hours

- Contacts for SAE reporting can be found on the protocol title page.
- Email is the preferred method to transmit SAE information.
- Facsimile transmission of the SAE information is also acceptable.
- In rare circumstances and in the absence of facsimile equipment, notification by telephone (see the study contact list) is acceptable with a copy of the SAE form, sent by overnight mail or courier service.
- Initial notification via telephone does not replace the need for the investigator to complete and sign the SAE form within the designated reporting time frames.

# CONFIDENTIAL JUVÉDERM® VOLUMA® with Lidocaine injectable gel

#### 10.7.6. Reporting of SADEs

#### SADE Reporting to Sponsor or Designee

NOTE: There are additional reporting obligations for medical device deficiencies that are potentially related to SAEs that must fulfil the legal responsibility to notify appropriate regulatory authorities and other entities about certain safety information relating to medical devices being used in clinical studies.

- Any device deficiency that is associated with an SAE must be reported to the sponsor within 24 hours after the PI determines that the event meets the definition of a device deficiency.
- The sponsor shall review all device deficiencies and determine and document in writing whether they could have led to an SAE. These shall be reported to the regulatory authorities and IECs as required by national regulations.
- Contacts for SAE reporting can be found on the protocol title page.

#### CONFIDENTIAL JUVÉDERM® VOLUMA® with Lidocaine injectable gel

### **10.8.** Appendix 8: Protocol Amendment History

The protocol amendment summary of changes table for the current amendment is located directly before the table of contents.

#### Amendment 2 (December 2020)

#### **Overall Rationale for the Amendment:**

The primary purpose of this protocol amendment is to update the safety laboratory assessments in alignment with the investigative sites' capabilities.

Section No. and Name	Description of Change	Brief Rationale
8.2 (Safety Assessments)	Removed the term Other as an injection site response listed in the participant's safety diary	Correction
8.2.1 (Clinical Safety Laboratory Assessments)	Revised the term laboratory manual to laboratory requirements	Correction
10.2 (Appendix 2)/Clinical Laboratory Tests/Table 10-1	For clinical chemistry assessments, removed the parameter indirect bilirubin , revised assessment of glucose from nonfasting to fasting glucose, and revised the parameter of blood urea nitrogen to urea nitrogen/urea	Correction
10.2 (Appendix 2)/Clinical Laboratory Tests/Table 10-1	For routine urinalysis, added the parameter bilinogen and revised the parameter leukocyte esterase by dipstick to leukocyte esterase/leukocyte neutrophil esterase/leukocyte	Correction

#### Amendment 1 (August 2020)

#### **Overall Rationale for the Amendment:**

The primary purpose of this protocol amendment was to update the needle size to include a 25 G 1" needle and update study processes as summarized below.

Section No. and Name	Description of Change	Brief Rationale
1.1/Synopsis	Added the option of using a 25 G 1" needle	Update
1.2/Schema	Added 'after randomization' after 'Optional treatment at Month 6' for the control group	Improve clarity
1.3/Schedule of Activities	Added that pregnancy test is to be administered prior to randomization (for participants in the control group)	Improve clarity
Table 1-3	Added 'After Randomization' in the column 'Month 1 (+1w), Month 3 (±2w), Month 6 (±2w)' for the control group	Improve clarity

Protocol 1878-701-008 Amd 3

CONFIDENTI	[AL		
JUVÉDERM ®	VOLUMA®	with Lidocaine i	njectable gel

Section No. and Name	Description of Change	Brief Rationale
Table 1-3	Added a pregnancy test at study exit and updated corresponding language in footnotes for the control group	Update
Table 1-3	Removed 3D imaging and vital sign assessments from the optional initial treatment visit due to duplication with that at Month 6 after randomization/study exit	Improve clarity
Table 1-3	Updated language in footnote h) to clarify the specific visit at which laboratory testing is to be conducted	Improve clarity
4.3/Justification for Dose	Added the option of using a 25 G 1" needle	Update
Table 6-1	Added the option of using 25 G 1" needles and clarified that they will be provided separately.	Update
6.1.2/Instructions for Use and Administration	Added the option of using a 25 G 1" needle	Update
8.1.1/Intervention Administration Assessments	Added that injection technique will be included in the evaluation of the study intervention	Update
8.1.1/Intervention Administration Assessments	Added the option of using a 25 G 1" needle	Update
8.2/Safety Assessments	Added description of how ISRs will be monitored	Update

# 1.0 Introduction

This Statistical Analysis Plan (SAP) provides a technical and detailed elaboration of the statistical analyses of the effectiveness and safety data as outlined and specified in the final protocol of Study 1878-701-008 (Amendment 3, 18 January 2022). Specifications of tables, figures and data listings are contained in a separate document.

Unless noted otherwise, all analyses will be performed using SAS Version 9.4 (SAS Institute Inc., Cary, NC 27513) or later under the LINUX operating system.

This SAP includes changes to analyses described in the protocol. Details are outlined in Appendix C.

# 2.0 Study Design and Objectives

## 2.1 Study Objectives

The objectives of this study are to evaluate the safety and effectiveness of VOLUMA with Lidocaine injectable gel in adult participants in Chinese population seeking correction of temple hollowing.

## 2.2 Study Design Overview

This is a prospective, multicenter, evaluator-blinded, randomized, parallel-group, notreatment controlled study to evaluate the safety and effectiveness of VOLUMA with Lidocaine HA injectable gel to correct temple hollowing. See Protocol Section 4.1 Overall Design for details.

The schematic of the study is shown in Figure 1.

#### Figure 1. Study Schematic

#### 2.3 Treatment Assignment and Blinding

Subjects will be randomized to VOLUMA with Lidocaine group (also referred as VOLUMA group in this document) or control group in a 2:1 ratio.

#### 2.4 Sample Size Determination

The primary effectiveness measure is the change from baseline on the 5-point ATHS at Month 6. The primary effectiveness variable is the ATHS responder status, which is determined by an improvement of 1 grade or more (i.e., a change score of -4 to -1) in both temples.

Under a 2:1 randomization ratio, a total of 90 participants in the treatment group and 45 participants in the control group at the primary timepoint will provide at least 90% power to detect a difference of 30% in the responder rates between the groups. This calculation is based on a 2-sided Fisher's exact test at the 5% level, using responder rates

of 65% and 35% for both temples simultaneously for participants in the treatment and control groups, respectively. The assumption of a 65% treatment responder rate is a conservative estimate based on the observed responder rate in previous filler studies for other facial areas. Also, while a 30% difference from control is greater than a minimally important difference, a 35% responder rate is a reasonable upper limit of expectation for the control group, based on validation results of the ATHS and control group responder rates observed in previous filler studies. Furthermore, assuming a dropout rate of 20% after randomization through the Month 6 visit, 168 randomized participants are needed, with 112 participants in the treatment group and 56 participants in the control group (2:1 ratio).

With 7 investigational sites planned, it is recommended that no site randomize more than approximately 42 participants (i.e., twice the proportional share of 1 more site =  $2 \times [168/8]$ ). The recommended minimum is 8 participants per site, which will guarantee that each treatment group has at least 2 participants at each site (allowing for mixed randomization blocks of 3 and 6 that incorporate the 2:1 randomization ratio).

The commercial software PASS (2008, Version 8.0.13) was used for the power calculation. The sample size calculation used an inequality test for 2 proportions to demonstrate that the treatment group is superior to the control group.

# 3.0 Endpoints

# 3.1 Primary Endpoint(s)

The primary endpoint is ATHS responder status based on the EI's live assessment at Month 6 during CP where a "responder" is a participant with at least 1-grade improvement on the ATHS in both temples.

#### 3.2 Secondary Endpoint(s)

Secondary endpoints are:

- Responder status for EI assessment of GAIS in the temple area at Month 6 during CP
- Responder status for participant assessment of GAIS in the temple area at Month 6 during CP
- Change from baseline in participant responses to FACE-Q Satisfaction with Facial Appearance questionnaire, for the Rasch-transformed score (0-100) at Month 6
- Change from baseline in participant responses to FACE-Q Satisfaction with Temples questionnaire, for the Rasch-transformed score (0-100) at Month 6 during CP

#### 3.3 Other Effectiveness Endpoint(s)

The additional effectiveness endpoints are for each visit unless specified otherwise.

- Primary and secondary endpoints at other visits
- Full-scale ATHS scores
- Full-scale EI assessment of GAIS
- Full-scale participant assessment of GAIS
- Responder status on the FACE-Q Satisfaction with Facial Appearance questionnaire, for the Rasch-transformed score, which will be summarized as a percentage of participants, where a responder is defined as a participant with an improved score from baseline
- FACE-Q Satisfaction with Facial Appearance questionnaire, for the Raschtransformed score (0-100) (i.e., raw score)
- Responder status on individual items, A (How symmetric your face looks?), F (How rested your face looks?), J (How your face looks when first wake up?) of the FACE-Q Satisfaction with Facial Appearance questionnaire, which will be

summarized as a percentage of responders, where a responder is defined as a participant who responds as Somewhat Satisfied or Very Satisfied

- Responder status on the FACE-Q Satisfaction with Temples questionnaire, for the Rasch-transformed score, which will be summarized as a percentage of participants, where a responder is defined as a participant with an improved score from baseline
- FACE-Q Satisfaction with Temples questionnaire, for the Rasch-transformed score (0-100) (i.e., raw score)
- Responder status on individual items, 2 (how full your temples look?), 4 (how your temples look in a mirror (straight on)?), 11 (how well the shape of your temples compliments the shape of your face?), 12 (the age your temples make you look?), of the FACE-Q Satisfaction with Temples questionnaires, which will be summarized as a percentage of responders, where a responder is defined as a participant who responds as Somewhat Satisfied or Very Satisfied
- Participant's satisfaction with treatment questions and age perception question
- Volume change of each temple (left temple, right temple) from baseline as assessed by 3D imaging

## 3.4 Safety Endpoint(s)

The safety endpoints will include procedural pain, ISRs, AEs, jaw function assessment, vital signs, concomitant medications and procedures, and clinical laboratory values.

## 3.5 Additional Endpoint(s)

Not applicable.

# 4.0 Analysis Populations

The analysis populations will consist of participants as defined in Table 1 below:

#### Table 1.Analysis Sets

Population	Definition	Study Intervention
Modified Intent -to Treat (mITT)	All randomized participants who have non-missing baseline ATHS assessment for both temples.	As randomized
Observed Primary Endpoint (OPE)	All mITT population participants who have non-missing Month 6 ATHS assessments for both temples.	As randomized
Per-Protocol (PP) All mITT population participants who have non-missing month 6 ATHS assessments for both temples and do not have any significant protocol deviations affecting the primary effectiveness endpoint. (i.e., a significant deviation that occurs after the primary endpoint does not lead to exclusion from the PP population.)		As randomized
Safety	All participants who are randomized and received study intervention (VOLUMA or no-treatment control).	As treated
VOLUMA Initially Treated (VIT)	All safety population participants who were randomized and received VOLUMA treatment at the beginning of the Control Period.	As treated
VOLUMA Optionally Treated (VOT)	All safety population participants who were randomized to control group and received VOLUMA optional treatment after the Control Period.	As treated

The number of participants in each of the 6 study populations (mITT, OPE, PP, Safety, VIT and VOT) will be summarized by treatment group, if applicable.

# 5.0 Participant Disposition

#### 5.1 Study Period

The study periods are defined below in Table 2 for VOLUMA group and control group. For VOLUMA group, the Treatment Period (TP) is the Control Period (CP) plus the Postcontrol Period (PCP). For participants in the control group, the TP starts on the date of delayed treatment and ends on the day of the study exit.

# Table 2.Definition of the Control and Treatment Periods by Analysis Group
(as-randomized for effectiveness or as-treated for safety)

Analysis Group	Period	Analysis Group Label	Start Date	End Date
VOLUMA	СР	VOLUMA	Initial treatment date	
 
The end date is the date of the Month 6 assessment:
 
If multiple assessments fall into Month 6 window, the date of the assessment included in the Month 6 analysis will be used as end date.
 
For participants who exit before Month 6, the end date is study exit date.
 
For participants with a missing assessment at Month 6, the end date is the target day for Month 6 (180 days from preceding treatment).
 

	TP	VOLUMA	Initial treatment date	Study exit date
Control	СР	Control	Randomization date	
 
For participants who do not receive optional treatment:
 
If multiple assessments fall into Month 6 window, the date of the assessment included in the Month 6 analysis will be used as end date.
 
For participants who exit before Month 6, the end date is study exit date.
 
For participants with a missing assessment at Month 6, the end date is the target day for Month 6 (180 days from preceding treatment).
 
For participants who receive optional treatment, the end date is the date when the treatment is received.
 

	ТР	VOLUMA Post-Control	Optional initial treatment date	Study exit date

For CP, effectiveness analyses and baseline characteristics will be performed on the mITT population using the "as-randomized" assignment.

For TP, effectiveness and safety summaries will be performed on the VIT and VOT population for each treatment group.

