# CONFIDENTIAL JUVÉDERM® VOLUMA® with Lidocaine injectable gel

Note: If the participant is not able to present in-clinic to the site due to national or regional travel restrictions, site closure as a result of these restrictions, or a participant declines an in-clinic visit due to pandemic or natural disaster-related health concerns, a telephone or virtual visit is permitted. However, if a participant is later able to present in-clinic to the site within the visit window, assessments may be performed in-clinic and the data will be captured for the visit.

- a All follow-up visits are scheduled from the date of the last treatment: If no touch-up treatment is performed, initial treatment will also be the last treatment.
- b All study exit procedures are to be performed for participants who withdraw from the study.
- c All screening procedures (including pregnancy test) must be performed before randomization; randomization must occur before initial treatment.
- d For female participants of childbearing potential; administered and confirmed negative before randomization or study intervention. Pregnancy testing need not be repeated if study pregnancy testing has been conducted within 7 days before randomization/initial treatment. In post-control period to be conducted only at study exit visit. A female participant is not considered of childbearing potential if she has been postmenopausal for at least 1 year or does not have a uterus at the time of study entry. Can be urine or blood pregnancy test according to site requirements.
- e The TI may perform a touch-up treatment if agreed upon by both the participant and TI. Touch-up treatment is recommended if the TI thinks that optimal correction has not been achieved.
- f Must be completed before randomization.
- g Must be completed before study interventions.
- h Performed at Month 6 visit only.
- i If participants exit the study before Month 6, then lab testing is needed at Exit Visit.
- j The 30-day daily safety diaries are to be completed following each treatment starting on the day of treatment and are considered complete if all days are completed until the visit 1 month after treatment.
- k Assessment on Day 14 after each treatment will be recorded along with safety diaries, while for other visits it will be performed on-site.

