#### Table 1-3 Cont

**Control Group Procedures** 

Procedure	Control Period		Post-control Period					
	Randomization (Day 1)	Telephone Call 3 (±2) Days After Randomization	Month 1 (+1 w), Month 3 (±2w), Month 6 (±2w) a After Randomization/ Study Exit a	Optional Initial Treatment (same day as Month 6 after Randomization Visit)	Telephone Call 3 (±2) Days after Initial Treatment	Optional Touch-up Month 1 (+1w) after Initial Treatment	Telephone Call 3 (±2) Days After Touch-up	Month 1 (+1 w), Month 3 ( $\pm 2w$ ), Month 6 ( $\pm 2w$ ) after last Treatment b Study Exit
Randomization c	Х							
Pregnancy test d	Х		Х	Х		X		Х
3D facial imaging	Xe		X			X f,g		Х
FACE-Q (Participant)								

 
Satisfaction with Temple
 
	Xe		х					х

 
Satisfaction with Facial
 
								
Appearance								
ATHS (EI)	Xe		X					X
Self-perception of age (Participant)	Xe							X
GAIS (Participant)			X					X
GAIS (EI)			X					X
Vital signs (blood pressure, pulse rate,			Х			$\mathbf{X}^{\mathbf{f}}$		Х
respiratory rate, temperature) (11)				v		Vg		
Study intervention (11)				A V		$\Lambda^{\circ}$		
Study intervention characteristics				Λ		Λ		
injection ease, product moldability				v		v		
(TI)				Λ		Λ		
Weight	x		x					x
Treatment satisfaction questions								
(Participant)								
Satisfaction with treatment								

 
Natural look and feel of the results
 
								
How treatment met expectation								Х

 
Likelihood of continuing the
 
								
treatment								

 
Willingness to recommend
 
								
treatment								
Laboratory testing (urinalysis,								$\mathbf{X}^{\mathrm{h}}$
hematology, chemistry)								21
Safety telephone call (TI)		X			X		X	
Safety 30-day diary i (Participant)				Х		Х		
Jaw Functional Limitation Scale	Xe			Xt		Xt		Xk
(Participant) j			~					
Adverse events (TI)	Continuous monitoring							
Concomitant medications, procedures,	, Continuous monitoring							
merapies (11)								

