#### 9.2.2 Adverse Event Overview

TEAEs will be summarized by treatment group for CP using the safety population. TEAEs will also be summarized by treatment group for TP using the VIT and VOT populations, respectively as described in Table 8. The summaries will be presented using number and percentage of participants with TEAEs as well as the number of events. Additional summaries may be provided when applicable.

An overall summary of TEAEs will be presented as described in Table 8.

A TEAE will be considered a treatment-related TEAE if the TEAE is deemed as related to the study procedure or the study device by the TI. Treatment-related AEs will be summarized by duration, severity, time to onset on/after the most recent treatment, and outcome.

The duration of an AE is defined as the end date of AE minus the start date of AE plus 1.

If more than 1 AE is coded to the same preferred term for a participant, the participant will be counted only once for that preferred term using the most severe and most related occurrence for the severity and relationship to study intervention summaries, respectively.

If the severity of a TEAE is missing, the maximum severity will be assigned to the event for the summary on severity. The value will be displayed as missing in the data listing.

If the relationship to the study intervention is missing for a TEAE, the event will be considered related to the study intervention for the summary. The value will be displayed as missing in the data listing.

Listings of all AEs, TESAEs, TEAEs leading to discontinuation, and death will be presented.

Endpoint	Description	Timing	Methodology
Overall summary	
 
Overall summary only for the following categories:
 
TEAEs
 
Treatment-related TEAEs
 
Treatment-related TEAEs at injection site
 
Treatment-related TEAEs not at injection site
 
TESAEs
 
Treatment-related TESAEs at injection site
 
Treatment-related TESAEs at injection site
 
Treatment-related TESAEs not at injection site
 
Treatment-related TESAEs not at injection site
 
TESAEs at injection site
 
Treatment-related TESAEs not at injection site
 
Treatment-related TESAEs not at injection site
 
TesAEs leading to study discontinuation
 
Deaths
 
	CP, TP	Frequency counts and percentages
TEAEs	

By SOC and PT

By SOC, PT, and maximum severity

	CP, TP	Frequency counts and percentages

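### The control-period adverse event window is about 17–21% longer for VOLUMA participants who have a touch-up, and the by-arm summary shows no follow-up time or common cut-off

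*SAP*

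**What the plan says.** SAP Section 5.1, Table 2, gives the control period a different start and end in each arm.

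- **VOLUMA:** it starts at "Initial treatment date", and for the end the table says "The end date is the date of the Month 6 assessment". Protocol Table 1-2, footnote a, schedules follow-up from the last treatment and adds: "If no touch-up treatment is performed, initial treatment will also be the last treatment". The touch-up is optional, at Month 1 (+1 week) after the initial treatment.
- **Control:** it starts at "Randomization date", and Protocol Table 1-3, footnote a, schedules control-period visits from randomization. For controls who go on to treatment, Table 2 says: "For participants who receive optional treatment, the end date is the date when the treatment is received". Protocol Table 1-3 places that treatment on the "same day as Month 6 after Randomization Visit", so it does not lengthen their window.

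SAP Section 9.2.2 states: "TEAEs will be summarized by treatment group for CP using the safety population". The measures are number and percentage of participants, and number of events. SAP Section 6.0 measures exposure as injected volume. Neither document plans a summary of follow-up time, a person-time rate, or a cut-off day shared by the arms.

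**The concern.** The control period is the only part of the trial in which adverse events under VOLUMA can be set beside a concurrent randomized untreated group. After Month 6, controls either leave or receive VOLUMA.

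Within that period, a VOLUMA participant with a touch-up is observed for about a month longer than a control. Events unrelated to the device (infections, incidental injuries and the like) keep accruing in that month. Percentages and event counts are both affected. A reader of the planned tables cannot see that the windows differ, and might take part of an excess in unrelated events for an effect of the device.

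**Working it through.** **Inputs**
- Month 6 target: 180 days (SAP Table 2), which is 6 × 30. The documents give no figure for the difference in control-period length.
- Touch-up: 30 days after initial treatment (Protocol Section 6), with a +1 week window (Protocol Table 1-2), so day 30 to day 37.
- Month 6 visit window: ±2 weeks in both arms, so day 166 to day 194 from the anchor date.
- Randomized: 112 VOLUMA and 56 control (Protocol Section 9.2).
- Touch-up share and background AE incidence: not given, so assumed below.

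**Window length, Month 6 visit on its target day**
- Control: 180 days.
- VOLUMA without touch-up: 180 days, excess 0%.
- VOLUMA, touch-up at day 30: 30 + 180 = 210 days; 30/180 = 16.7% longer.
- VOLUMA, touch-up at day 37: 37 + 180 = 217 days; 37/180 = 20.6% longer.

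Other conventions give other figures. With the touch-up at day 37 and both arms' Month 6 visits two weeks late, the lengths are 231 and 194 days (37/194 = 19.1%). Single pairs of participants can differ by anything from 196 against 194 days (+1.0%) to 231 against 166 days (+39.2%). Much of that spread is the visit window, which applies to both arms.

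**Mean excess in the VOLUMA arm** = share with touch-up × (30 to 37)/180

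| Assumed touch-up share | Mean excess |
|---|---|
| 25% | 4.2–5.1% |
| 50% | 8.3–10.3% |
| 75% | 12.5–15.4% |

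**Effect on a crude percentage.** Assume a constant background hazard. If a proportion p has an event in 180 days, the proportion over L days is 1 − (1 − p)^(L/180).

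| p over 180 days | 210 days | 217 days |
|---|---|---|
| 10% | 11.6% | 11.9% |
| 20% | 22.9% | 23.6% |

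For p = 20% the excess in a touch-up participant is 2.92 points at 210 days and 3.59 points at 217 days. With a 50% touch-up share and touch-up at day 30, the arm-level shift is 0.5 × 2.92 = 1.46, about 1.5 points.

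**Against the trial's precision.** The standard error of a difference in proportions at 20% is √[0.20 × 0.80 × (1/112 + 1/56)] = 6.5 points. The shift of about 1.5 points is about 0.2 standard errors. If every VOLUMA participant had a touch-up, it would be 2.92/6.5 = 0.45 standard errors at day 30, or 3.59/6.5 = 0.55 at day 37.

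**The case against.** The case for leaving the plan alone is substantial.

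- **No formal comparison.** No between-arm test, confidence interval or margin is planned for AEs; the gatekeeping covers only ATHS and GAIS. This stands. A reader might infer that the plan formally compares AE rates over unequal windows, but the documents plan only descriptive summaries.
- **Small and conservative.** The shift is a fraction of a standard error on the assumptions above, and it counts against VOLUMA. This also stands. A reader might take 17–21% as the excess for the whole arm. It applies only to participants with a touch-up; the others have none.
- **Device safety is read elsewhere.** Treatment-related TEAEs are split by injection site and by time from the most recent treatment, ISRs are recorded by treatment, and SAP Table 3 reports how many had a touch-up. This is true, but none of it puts the randomized contrast on a common window.
- **Further output is possible.** SAP Section 9.2.2 allows additional summaries, and table specifications are in a separate document not available here. That permits a common-window table without committing to one.
- **The anchor is deliberate.** Counting from the last treatment serves the effectiveness assessment, and the SAP follows it consistently. That is a reason to keep the visit schedule, and it does not prevent an additional safety table on a common window.
- **Person-time rates can mislead.** Injection-related events are expected to cluster after treatment. Dividing the same events by 210 days instead of 180 lowers the rate by 1 − 180/210 = 14% with no change in harm. This stands, and it limits what should be asked for.

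**Conclusion.** The asymmetry is real and follows directly from SAP Table 2 and the protocol's visit anchors. The control period is about 17–21% longer (210–217 against 180 days) for VOLUMA participants with a touch-up, and no longer for the rest. The arm-level mean excess is about 4–5%, 8–10% or 12–15% at touch-up shares of 25%, 50% or 75%.

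The consequence is a slight inflation of unrelated background TEAEs in the VOLUMA arm, of about 1.5 points if background incidence is 20% over 180 days, the hazard is constant, half have a touch-up, and it falls at day 30. These are assumptions; the documents give neither the share nor the incidence.

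The primary endpoint is not affected, and nothing here makes the device look safer than it is. The point is minor and worth acting on because the change is inexpensive.

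**What to change.** In SAP Section 9.2.2 and Table 8:

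1. Add control-period duration by arm: mean, median and total participant-months.
2. Add one control-period TEAE table by arm, counting events from Day 1 to the earlier of Day 180 and the control-period end date. The earlier-of rule is needed because a control's Month 6 visit, and with it optional treatment, can fall from day 166.
3. Keep the full-period tables as primary.

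Exposure-adjusted rates, if shown at all, should be supplementary and limited to overall and unrelated TEAEs. Table 10 needs no change; it is a check on one site's AE reporting.

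The cost is one extra table and a few rows, from dates already collected. There are two limits. The Day 180 cut covers only 143–150 days after a touch-up (180 − 37 and 180 − 30), which is why the full-period tables stay. The cut also does not lengthen windows that end early: a control seen at day 166 still has 14 days less than a touch-up participant followed to Day 180 (14/166 = 8.4%). The duration summary would show how much of this remains.

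The same edit can correct a wording slip in Table 2. For controls with a missing Month 6 assessment it says "the end date is the target day for Month 6 (180 days from preceding treatment"), but controls have no preceding treatment in the control period, so the count should refer to randomization.
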